2. LIST OF ABBREVIATIONS

Include a list of all abbreviations used in the TSAP

Term	Definition / description
[REDACTED]	[REDACTED]
ADS	Analysis data sets
AE	Adverse event
AGI	Alpha-glucosidase inhibitors
ALT	Alanine transaminase
[REDACTED]	[REDACTED]
[REDACTED]	[REDACTED]
AST	Aspartate transaminase
BIcMQ	Boehringer Ingelheim customized MedDRA Query
BMI	Body Mass Index
BRPM	Blinded report planning meeting
CI	Confidence Interval
CT	Concomitant therapies
CTP	Clinical Trial Protocol
CTR	Clinical Trial Report
(e)CRF	(Electronic) Case Report Form
DBL	Database Lock
[REDACTED]	[REDACTED]
ECG	Electro-cardiogram
EMA	European Medicines Agency
EoT	End of treatment
FAS	Full analysis set
FPG	Fasting Plasma Glucose
GPSP	Good Post-Marketing Study Practice
GVP	Good Vigilance Practice
HbA _{1c}	Glycosylated Haemoglobin
HBGM	Home blood glucose monitoring
HLT	Higher Level Term

Term	Definition / description
ICH	International Conference on Harmonisation
█	█
ITT	Intention-to-Treat
IRT	Interactive Response Technology
LOCF	Last observation carried forward
MedDRA	Medical Dictionary for Regulatory Activities
MI	Multiple Imputation
MMRM	Mixed model repeated measures
O*C	Oracle Clinical
OC	Observed Cases
█	█
█	█
PHQ	Patient Health Questionnaire
PK	Pharmacokinetics
PPS	Per protocol set
PSTAT	Project Statistician
PT	Preferred term
PV	Protocol violation
Q-Q	Quantile-Quantile
ROC	Rescue observed cases
SD	Standard deviation
SLUMS	Saint Louis University Mental Status exam
SMQ	Standardised MedDRA query
SOC	System organ class
TCM	Trial Clinical Monitor
TOC	Table of contents
TMW	Trial Medical Writer
TSAP	Trial statistical analysis plan
ULN	Upper limit of normal

3. INTRODUCTION

As per ICH E9, the purpose of this document is to provide a more technical and detailed elaboration of the principal features of the analysis described in the protocol, and to include detailed procedures for executing the statistical analysis of the primary and secondary variables and other data.

This TSAP assumes familiarity with the Clinical Trial Protocol (CTP), including Protocol Amendments. In particular, the TSAP is based on the planned analysis specification as written in CTP Section 7 “Statistical Methods and Determination of Sample Size”. Therefore, TSAP readers may consult the CTP for more background information on the study, e.g., on study objectives, study design and population, treatments, definition of measurements and variables, planning of sample size and randomisation.

SAS[®] Version 9.4 or later version will be used for all analyses.

4. CHANGES IN THE PLANNED ANALYSIS OF THE STUDY

The following modifications regarding the analysis of trial data are implemented:

Analysis specified in CTP	Adjusted Analysis specified in TSAP
Primary endpoint: Baseline insulin is fixed categorical effect.	Primary endpoint: Baseline basal insulin is linear continuous covariate.
[REDACTED]	[REDACTED]
[REDACTED]	[REDACTED]
[REDACTED]	[REDACTED]

Due to an alignment of terminology on project level, it was necessary to re-phrase some endpoints in the TSAP.

Analysis: Text in CTP	Analysis: Adjusted text in TSAP
Secondary endpoint: Proportion of patients experiencing at least one confirmed hypoglycaemic event during 24 weeks of treatment.	Proportions of patients experiencing at least one hypoglycaemia accompanied by a glucose value during 24 weeks of treatment.
[Redacted]	[Redacted]
[Redacted]	[Redacted]
[Redacted]	[Redacted]
[Redacted]	[Redacted]
[Redacted]	[Redacted]
[Redacted]	[Redacted]

5. ENDPOINTS

5.1 PRIMARY ENDPOINT

The primary endpoint in this study is the change from baseline in HbA_{1c} (%) after 24 weeks of randomised treatment.

5.2 SECONDARY ENDPOINTS

5.2.1 Key secondary endpoints

There are no key secondary endpoints in this trial.

5.2.2 Secondary endpoints

Secondary endpoints are the following:

- Proportion of patients experiencing at least one hypoglycaemia accompanied by a glucose value during 24 weeks of treatment. Hypoglycaemia accompanied by a glucose value is defined as
 - any investigator reported asymptomatic hypoglycaemic event or AE with a reported blood glucose measurement less than 54 mg/dL (<3.0mmol/L)
[*AE.SYMI=0 and ((AE.GLUCOSE <54 and AE.LABU=232) or (AE.GLUCOSE <3.0 and AE.LABU=301))*]
or
[*HYPOASYM.GLUCOSE <54 and HYPOASYM.LABU=232) or (HYPOASYM.GLUCOSE <3.0 and HYPOASYM.LABU=301)]*
 - or
 - any investigator reported symptomatic hypoglycaemic AE confirmed by a reported blood glucose measurement less than or equal to 70 mg/dL (≤ 3.9 mmol/L)
[*AE.SYMI=1 and ((AE.GLUCOSE ≤70 and AE.LABU=232) or (AE.GLUCOSE ≤3.9 and AE.LABU=301))*]
 - or
 - a severe hypoglycaemic AE, i.e.,, an event that requires the assistance of another person to actively administer carbohydrates or glucagon because the patient is unable to take the substance on his or her own.
[*AE.ASSIST=1*]

[figure not shown]
Note: If another person hands the carbohydrate or glucagon to the patient without having to actively administer the substance because the patient is able to take the substance on his or her own, the hypoglycaemic AE does not qualify as severe.

[figure not shown]
Note:

[figure not shown]
[figure not shown]
- (i) Hypoglycaemias are counted only once, i.e., a severe episode that has also symptoms indicated on the CRF is counted only once.
- (ii) If *AE.SYMI* is missing and $((AE.GLUCOSE < 54 \text{ and } AE.LABU=232) \text{ or } (AE.GLUCOSE < 3.0 \text{ and } AE.LABU=301) \text{ and } AE.ASSIST \neq 1)$, then the patient is considered for this analysis.

If *AE.SYMI* is missing and $[((AE.GLUCOSE \geq 54 \text{ and } AE.LABU=232) \text{ or } (AE.GLUCOSE \geq 3.0 \text{ and } AE.LABU=301) \text{ or } AE.ASSIST \neq 1)]$, then the patient is not considered for this analysis.

- Proportion of patients with HbA_{1c} on treatment <8.0% after 24 weeks of treatment.
- Proportion of patients with HbA_{1c} on treatment <7.0% after 24 weeks of treatment.
- Proportion of patients with HbA_{1c} lowering by at least 0.5% after 24 weeks of treatment.
- Change from baseline in FPG (mg/dL) after 24 weeks of treatment.

6. GENERAL ANALYSIS DEFINITIONS

6.1 TREATMENTS

In this section, the treatment set-up (treatment regimens/study intervals and randomised treatment) is defined.

6.1.1 Treatment regimens / study intervals

There will be five treatment phases in this trial: screening, placebo run-in, treatment, post-treatment and post-trial.

The purpose of the table below is to describe all the different trial/treatment intervals, in which a patient can lie during the course of the trial. Note that the term “treatment regimen” can also cover time periods with no active treatment.

Table 6.1.1: 1 Treatment regimens / study intervals (Analno 1)

Short label	Interval	Sort order	Start date / Start time (HH:MM)	End date / End time (HH:MM)
Screening	Screening	1	Date of informed consent / 00:00	Date of first administration of run-in medication / 00:00
Run-in	Run-in	2	Date of first administration of run-in medication / 00:00	Date and time of first administration of study medication
Placebo / Lina 5mg	On-treatment	3 / 4	Date of first administration of study medication / Time of first administration of trial medication – if missing: 12:00 noon	Last day of trial medication intake + 1day, 00:00
Post treat	Post-treatment	5	last day of trial medication intake +1day, 00:00	Date of V99 +1day, 00:00
Post-trial	Post-trial	6	Date of V99 +1day, 00:00	

For purposes of the analysis, the residual period for assigning measurements to the on-treatment period is dependent on the endpoint and therefore the analysis is based on visit windows as opposed to treatment regimens. Visit windows are further defined in [Section 6.7](#).

6.1.2 Randomised treatment

Patients who receive an incorrect treatment at any visit (one which they were not randomised to) will be analysed for both efficacy and safety under the treatment which they were randomised to, for the entire trial period.

A special listing of Adverse Events only for patients that took a wrong treatment between visits within the course of the trial will be created.

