**Proprietary confidential information.**

© 2015 Boehringer Ingelheim International GmbH or one or more of its affiliated companies. All rights reserved.

This document may not - in full or in part - be passed on, reproduced, published or otherwise used without prior written permission.

[REDACTED] A protocol violation will be considered important if it can be expected to have a distorting influence on the assessment of the primary endpoint.

Important protocol violations include:

- Randomised study medication: incorrect study medication taken
- Severe violation of treatment compliance
- Severe violation of inclusion criteria
- Non-adherence to other specifications of the protocol that could bias the primary endpoint

Further details will be given in the Trial Statistical Analysis Plan (TSAP).

All patients treated with at least one dose of study medication (the Treated Set) will be included in the safety evaluation.

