### 7.3.3 Safety analyses

All safety data will be displayed and analysed using descriptive statistical methods. Depending on the character of the individual safety endpoint, the most appropriate way to summarize the results as frequency tables for categorical data or descriptive statistics for continuous data will be used. No formal inferential analysis is planned for safety comparison.

AEs will be coded using the Medical Dictionary for Drug Regulatory Activities (MedDRA) coding dictionary. All events with an onset after the first dose of study medication up to a period of seven days after the last dose of study medication will be assigned to the treatment phase for evaluation. This includes AEs that start before first study medication intake and deteriorate under treatment. Other AEs will be assigned either to the screening, run-in, or follow-up phase as appropriate. Safety analyses will be performed on the TS, with patients assigned to the treatment they were randomised to. Additional listings based on actual treatment at onset of AE will be produced for patients who receive incorrect treatment at any point throughout the trial.

Laboratory values taken after the first dose of randomised treatment up to a period of seven days after the last intake of treatment will be assigned to the treatment phase for evaluation. Laboratory values will be compared to their reference ranges and frequency tables will be provided for the number of patients within and outside the reference range.

Changes from baseline in blood pressure and pulse rate will be summarised by treatment group.

Further details on the safety analysis will be specified in the TSAP.

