**A total of 300 patients will be randomised.**

Proprietary confidential information.

© 2015 Boehringer Ingelheim International GmbH or one or more of its affiliated companies. All rights reserved.

This document may not - in full or in part - be passed on, reproduced, published or otherwise used without prior written permission.

Based on pooled data from the 1218.36 and 1218.63 trials [REDACTED] assuming a standard deviation of 1.2% in both groups in the FAS with a 0.77% difference in HbA1c change from baseline in treatments, a number of 150 patients in each treatment arm will show superiority with a power >99%. This determination of power is based on a Student's t-test and a two-sided significance level of 5%.

Software package nQuery version 7.0 was used to derive the sample size.

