A5.2	Depressed mood	Exclusion criteria 2 checked and/or Patient Health Questionnaire (PHQ) score ≥10 at Visit 1.	None	S
A5.3	Acute pancreatitis or Chronic pancreatitis	Germany only. Exclusion criteria 19 checked and/or Diagnosis of acute pancreatitis within 3 months of screening and/or Medical history of chronic pancreatitis.	None	S
B	Informed consent			
B1	Informed consent not available/not done	Inclusion criteria 1 not met and/or Date of informed consent for the study missing and/or No signature on patient's "Declaration of Informed Consent" Patient's data will not be used at all.	All	R

Table 6.2: 1 Important protocol violations (cont.)

Category/ Code	Description	Example/Comment	Excluded from	T ⁺
B	Informed consent			
B2	Informed consent too late	Date of informed consent for the study not obtained prior to any study related procedure or re-consent with new version of informed consent too late. Minimum requirement for initial informed consent <= date of Visit 1/date of any study procedure.	None	S
B3	Informed consent for sub-study not available	No separate informed consent for DNA banking (unspecified DNA sample). Note: Pre-specified DNA and RNA samples are covered by the trial informed consent and therefore no additional informed consent is required. In Australia and the UK pre-specified DNA sample is forbidden according to local amendment. Patient's unspecified DNA sample will not be retained or analysed. For Australia and UK, the pre-specified DNA will not be retained or analysed.	None	S
C	Trial medication and randomisation			
C1	Incorrect trial medication taken			
C1.1	No trial medication taken	Patient randomised but no trial medication taken.	TS, FAS and PPS	E
C1.2	Incorrect trial medication taken	Wrong medication taken (different medication than the patient was randomised to taken at any visit, i.e. drug kit recorded in eCRF from different treatment group than drug kit assigned by the interactive response technology (IRT) and/or Gross misuse of trial medication (e.g. unacceptable dose of trial medication). Can only be finally judged after DBL since unblinding information is required.	PPS	E
C2	Randomisation not followed			
C2.1	Treated without randomisation	Patient treated according to eCRF, but not randomised according to IRT.	RS, FAS and PPS	E

Table 6.2: 1 Important protocol violations (cont.)

Category/ Code	Description	Example/Comment	Excluded from	T ⁺
C3	Non-compliance			

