6.3 PATIENT SETS ANALYSED

- **Randomised set (RS):**
This patient set includes all randomised patients, whether treated or not.
- **Treated set (TS):**
This patient set includes all patients who were dispensed study medication and were documented to have taken at least one dose of investigational treatment.
- **Full analysis set (FAS):**
This patient set includes all patients randomised in the TS who have a baseline and at least one on-treatment HbA_{1c} value.
- **FAS-completers-24 (FASC24):**
This patient set includes all patients in the FAS who complete a minimum treatment duration of 149 days, did not prematurely discontinue the trial and have an available HbA_{1c} measurement within the time window for the Week 24 visit (Visit 98 for non-Japanese and Visit 7 for Japanese patients up to day 176). This analysis set is not required for the analysis at Week 52. See [Table 6.7: 1](#).
- **Per protocol set (PPS):**
This patient set includes all patients in the FAS who do not have any IPVs relating to efficacy, cf. [Table 6.2: 1](#).

Table 6.3: 1 Patient sets analysed

Class of endpoint	Patient set			
	TS	FAS	PPS	FASC24
Primary endpoint		Primary analysis	Sensitivity analysis	Sensitivity analysis
Secondary and further endpoints		X		
Safety endpoints	X			
Demographics	X			
Baseline efficacy variables		X		

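### On-treatment safety data follow the randomised arm without exception, so treated-but-never-randomised patients have no column and patients who took only the other arm's kits are tabulated under a drug they never took

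*SAP*

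**What the plan says.** **Arm rule.** SAP 6.1.2 covers patients who receive a treatment other than the one assigned: they "will be analysed for both efficacy and safety under the treatment which they were randomised to, for the entire trial period". Protocol 7.3.3 has the same rule: "Safety analyses will be performed on the TS, with patients assigned to the treatment they were randomised to". SAP 6.7 and 7.8.1 repeat it for on-treatment measurements and for adverse events from first intake to 7 days after last intake. Events outside that interval go to the screening or post-treatment phase.

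**Who is in the safety set.** SAP 7.8 runs all safety analyses on the Treated Set (TS). SAP 6.3 admits a patient who was dispensed medication and was "documented to have taken at least one dose of investigational treatment"; randomisation is not a condition. Protocol 7.3 says: "All patients treated with at least one dose of study medication (the Treated Set) will be included in the safety evaluation".

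**Code C2.1.** SAP Table 6.2: 1 defines it as "Patient treated according to eCRF, but not randomised according to IRT" and excludes such patients from the randomised set, FAS and PPS. The TS is not on that list.

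**Listings.** SAP 6.1.2 plans a special adverse-event listing for patients who took a wrong treatment. Protocol 7.3.3 plans additional listings for the same kind of patient, organised by the treatment the patient was actually receiving when the event began. The SAP text does not carry over that last feature.

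**The concern.** The only arm rule in view needs a randomised treatment, and the safety set can contain patients who have none. As written, a C2.1 patient counts in the TS but belongs to neither column. A programmer would have to choose one, possibly after unblinding.

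An exclusively wrong-kit patient does get a column, but it is that of a drug the patient never took. Misplacing exposure in this way tends to pull the arms together. For safety that is the non-conservative direction, and safety and tolerability are stated objectives (protocol 2.2). Rare events of special interest are the most exposed, because one patient can change the picture. Efficacy has a set that removes wrong-medication patients (code C1.2 leads to exclusion from the PPS); no visible safety table has a counterpart.

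**Working it through.** **1. The plan's own figure.** Protocol 7.6 states that "150 patients in each treatment arm will show superiority with a power >99"%, "assuming a standard deviation of 1.2% in both groups in the FAS with a 0.77% difference" in HbA1c change, using a "Student's t-test and a two-sided significance level of 5"%. The noncentrality is 0.77 / (1.2 × √(2/150)) = 5.557 on 298 degrees of freedom, which gives a power of 0.9998. The figure reproduces. The point does not depend on it; only the 150 per arm is used below.

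**2. Does C2.1 stay in the TS?** Two rows of SAP Table 6.2: 1, side by side:

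| Code | Situation | Excluded from |
|---|---|---|
| C1.1 | randomised, no medication taken | TS, FAS, PPS |
| C2.1 | treated, not randomised | RS, FAS, PPS |

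The table names the TS when it means the TS. SAP 6.3 also limits the FAS to patients in the TS who were randomised, a qualifier that would be unnecessary if everyone in the TS had been randomised. So C2.1 patients remain in the TS.

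**3. Which column does each type of patient enter?**

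| Patient in the TS | Column under the plan | Matches the drug taken? |
|---|---|---|
| Correct kits throughout | randomised arm | yes |
| Wrong kit at some visits (mixed exposure) | randomised arm | partly |
| Only the other arm's kits | randomised arm | no |
| C2.1 | none defined | not applicable |

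The last two rows are the problem. SAP Table 6.3: 1 also puts demographics on the TS, so the missing column for C2.1 patients reaches those tables too.

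**4. Do the listings close the gap?** They disclose wrong-treatment cases but do not change any table. Both are worded for patients who took something other than their assigned treatment. A C2.1 patient has no assigned treatment to deviate from, so coverage is unclear.

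**5. Size.** The documents give no count of either type. Assume 150 per arm and an incidence of 2% (3 events) or 5% (7.5 expected events) in each arm.

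*Exclusively wrong-kit patient with an event.* With denominators held at 150, moving the patient changes the risk difference by 2/150 = 1.33 points. Letting the denominators move as well:
- 2%: 4/151 − 2/149 = 2.65% − 1.34% = 1.31 points
- 5%: 8.5/151 − 6.5/149 = 5.63% − 4.36% = 1.27 points

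All three are about 1.3. Three such patients, denominators held, would give 6/150 = 4.0 points. In a rare-event table, a 2 versus 0 split by drug taken would be shown as 1 versus 1 if one of the two patients had been randomised to the other arm.

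*C2.1 patient with an event.* This patient leaves no column and is only added to one:
- 2%: 4/151 = 2.65%, a rise of 0.65 points
- 5%: 8.5/151 = 5.63%, a rise of 0.63 points

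**The case against.** The strongest reply is that as-randomised safety assignment is a disclosed, prespecified rule on which protocol and SAP agree, with a listing for the affected patients in both. Protocol 7.3.3 plans no formal inferential comparison of safety. That stands: a reader might infer a contradiction or an error in the rule, and the documents support neither.

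A reader might also infer that every wrong-kit patient is reported under a drug never taken. They do not support that either. Code C1.2 is met by one wrong kit at any visit. Medication is dispensed on four occasions (protocol 4.1.4) with a new number each time (protocol 6.2.2), so a single error produces mixed exposure. Such a patient did take the randomised drug and would not move under the fix below.

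Nor is the protocol's inclusion of all treated patients broken. C2.1 patients are in the TS; what they lack is a column. The argument that misplacement pulls the arms together, and the 1.3-point shift, do not apply to them.

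Finally, C2.1 should be very rare, because allocation and kit numbers run through IRT, and SAP 6.2 takes set exclusions to the database-lock meeting. Rarity is a fair reason for low priority. But that meeting decides who leaves a set, not which column a remaining patient enters, so it does not fill the gap. Taken alone, the C2.1 gap is close to a missing detail.

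**Conclusion.** The point holds in a narrow form. Two groups are poorly served by the arm rule for the safety tables: C2.1 patients, who have no arm, and patients who took exclusively the other arm's drug, who have the wrong one. Screening and post-treatment events, mixed-exposure patients and the primary analysis are outside it; the FAS requires randomisation.

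The effect is about 1.3 percentage points in a risk difference per exclusively wrong-kit patient with an event, and about 0.6 to 0.7 points in one arm per C2.1 patient with an event. These figures rest on 150 per arm and, for C2.1, on an assumed 2% to 5% incidence. The number of such patients is unknown and may be zero, so the actual effect may be nil. This is a cheap improvement to essentially descriptive tables, not a threat to the trial's conclusions. It rests on the visible text; redacted SAP sections are not counted as missing.

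**What to change.** Amend SAP 6.1.2 before unblinding:

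- Keep as-randomised assignment for efficacy.
- For the safety tables on the TS, place C2.1 patients and patients who took exclusively the other arm's drug under the treatment actually taken, read from recorded kit numbers after database lock. Protocol 4.1.2 already has medication numbers entered in the eCRF.
- Keep mixed-exposure patients in their randomised arm.
- Restore the protocol's feature of listing events by the treatment actually being taken at onset, and extend that listing to C2.1 patients.
- State whether demographics on the TS follow the same rule.
- Record the departure from protocol 7.3.3 in SAP section 4.

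The cost is one paragraph and one derived variable. The downside is that safety and efficacy denominators may differ by a few patients. If demographics follow actual treatment, they may also differ slightly from the baseline efficacy tables on the FAS, which stay as randomised.

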		Inclusion criteria 3 not met and/or HbA _{1c} <7.5% if version 1 of informed consent signed, <7.0% if version 2 of informed consent signed or >10.0% at Visit 1 (>9.0% for Germany).		
	A2.2	Age out of range at screening	PPS	E
		Inclusion criteria 2a not met and/or age <70 years if version 1 of informed consent signed or <60 years if version 2 of informed consent signed at Visit 1.		
	A2.3	Body mass index out of range at screening	PPS	E
		Inclusion criteria 4 not met and/or Body mass index (BMI) >45kg/m ² at Visit 1.		
A3, A4, A5	Exclusion criteria violated			
	A3.1	Relevant concomitant diagnoses	None	S
		Exclusion criteria 4 checked and/or Acute coronary syndrome, stroke or TIA recorded on concomitant diagnoses eCRF within 3 months prior to Visit 1.		

Table 6.2: 1 Important protocol violations (cont.)

Category/ Code	Description	Example/Comment	Excluded from	T ⁺
A3.2	Impaired hepatic function	Exclusion criteria 5 checked and/or Alanine Transaminase (ALT) or Aspartate Transaminase (AST) or alkaline phosphatase > 3x upper limit of normal (ULN) during screening and/or run-in [Gilbert-Meulengracht syndrome is permitted].	None	S
A3.3	Known hypersensitivity to any of the drugs in the study regimen	Exclusion criteria 12 checked.	PPS	E S
A3.4	Treatment with protocol excluded antidiabetic drugs	Exclusion criteria 9 or 10 or 11 checked and/or Treatment with GLP-1 analogues within 3 months prior to informed consent (Visit 1) and/or Treatment with sulphonylureas, thiazolidinediones, SGLT2 inhibitors, or DPP-4 inhibitors within 3 months prior to randomisation (Visit 3) and/or Treatment with rapid acting or short acting insulin and/or pre-mixed insulin containing rapid acting or short acting insulin within 3 months prior to randomisation (Visit 3).	PPS	E
A3.5	Treatment with protocol excluded anti-obesity drugs	Exclusion criteria 13 checked and/or Intake of any of the excluded drugs reported on the eCRF within the time prior to informed consent specified in the exclusion criteria.	PPS	E
A3.6	Diagnosis of Type 1 Diabetes Mellitus	Exclusion criteria 3 checked and/or Type 1 Diabetes Mellitus on concomitant diagnoses eCRF.	PPS	E
A4.1	Treatment with any drugs that have significant effect on glucose metabolism, protocol excluded systemic steroids or change in thyroid hormone dose	Exclusion criteria 14 checked and/or Intake of any of the excluded drugs reported on the eCRF within the time prior to informed consent specified in the exclusion criteria.	PPS	E

Table 6.2: 1 Important protocol violations (cont.)

Category/ Code	Description	Example/Comment	Excluded from	T ⁺
A4.2	Alcohol or drug abuse that may interfere with study participation	Exclusion criteria 15 checked.	PPS	E
A4.3	Participation in another trial with an investigational drug within 2 months prior to informed consent	Exclusion criteria 16 checked Final decision at the DBL meeting (medical judgment), depending on the type of drug given in the prior trial (only if investigational drug interferes with glucose metabolism).	PPS	E
A4.4	Patient has undergone bariatric surgery within 2 years prior to informed consent	Exclusion criteria 6 checked and/or Evidence of surgery reported on eCRF.	None	E
A4.5	Medical history of cancer (except basal cell carcinoma) within 5 years prior to informed consent	Exclusion criteria 7 checked.	None	S
A4.6	Unstable Red Blood Cells	Exclusion criteria 8 checked and/or Diagnosis of blood dyscrasias or any disorder causing hemolysis or unstable red blood cells (e.g., malaria, babesiosis, haemolytic anaemia) listed on concomitant diagnoses page of eCRF.	None	E
A4.7	Psychological, familial, sociological, or geographical factors potentially hampering compliance with the protocol, visits, or trial procedures or any other clinical condition that would jeopardize patient safety while participating in this clinical trial in the opinion of the investigator	Exclusion criteria 17 checked.	None	S
A4.8	Inability to commit to regular overnight fasting of at least 10 hours duration and attendance to trial site visits between 07:00 and 11:00am	Exclusion criteria 18 checked.	PPS	S

Table 6.2: 1 Important protocol violations (cont.)

Category/ Code	Description	Example/Comment	Excluded from	T ⁺
A5.1	Impaired cognitive ability	Exclusion criteria 1 violated and/or Saint Louis University Mental Status (SLUMS) score of 21-26 (high school education) or 20-24 (no high school education) and no confirmation from investigator to rule out cognitive impairment. and/or SLUMS score of 20 or less (high school education) or 19 or less (no high school education) indicating dementia. Note: The first version of the eCRF contained the following statement: Saint Louis University Mental Status (SLUMS) Examination scores of 25 or less for those patients with high school education or 23 or less for those patients who did not complete a high school education indicate that the patient probably have impaired cognitive ability. [CONDT.PROTAM = 1.0 or 2.0]	None	S
A5.2	Depressed mood	Exclusion criteria 2 checked and/or Patient Health Questionnaire (PHQ) score ≥10 at Visit 1.	None	S
A5.3	Acute pancreatitis or Chronic pancreatitis	Germany only. Exclusion criteria 19 checked and/or Diagnosis of acute pancreatitis within 3 months of screening and/or Medical history of chronic pancreatitis.	None	S
B	Informed consent			
B1	Informed consent not available/not done	Inclusion criteria 1 not met and/or Date of informed consent for the study missing and/or No signature on patient's "Declaration of Informed Consent" Patient's data will not be used at all.	All	R

Table 6.2: 1 Important protocol violations (cont.)

Category/ Code	Description	Example/Comment	Excluded from	T ⁺
B	Informed consent			
B2	Informed consent too late	Date of informed consent for the study not obtained prior to any study related procedure or re-consent with new version of informed consent too late. Minimum requirement for initial informed consent <= date of Visit 1/date of any study procedure.	None	S
B3	Informed consent for sub-study not available	No separate informed consent for DNA banking (unspecified DNA sample). Note: Pre-specified DNA and RNA samples are covered by the trial informed consent and therefore no additional informed consent is required. In Australia and the UK pre-specified DNA sample is forbidden according to local amendment. Patient's unspecified DNA sample will not be retained or analysed. For Australia and UK, the pre-specified DNA will not be retained or analysed.	None	S
C	Trial medication and randomisation			
C1	Incorrect trial medication taken			
C1.1	No trial medication taken	Patient randomised but no trial medication taken.	TS, FAS and PPS	E
C1.2	Incorrect trial medication taken	Wrong medication taken (different medication than the patient was randomised to taken at any visit, i.e. drug kit recorded in eCRF from different treatment group than drug kit assigned by the interactive response technology (IRT) and/or Gross misuse of trial medication (e.g. unacceptable dose of trial medication). Can only be finally judged after DBL since unblinding information is required.	PPS	E
C2	Randomisation not followed			
C2.1	Treated without randomisation	Patient treated according to eCRF, but not randomised according to IRT.	RS, FAS and PPS	E

Table 6.2: 1 Important protocol violations (cont.)

Category/ Code	Description	Example/Comment	Excluded from	T ⁺
C3	Non-compliance			
C3.1	Non-compliance with drug intake	Gross non-compliance issues only – based on compliance section of eCRF (at least two times on treatment compliance was outside 80-120% according to eCRF) Final decision at the DBL meeting (medical judgment).	PPS	E
C3	Non-compliance			
C3.2	Non-compliance with criteria for removal from trial	Criteria for removing a patient from the trial not adhered to. Final decision at the DBL meeting (medical judgment).	None	E
C3.3	Treatment interruption for more than 10 consecutive days	Documented treatment interruption for 11 consecutive days or more.	PPS	E
C3.4	Non-compliance with HBGM data collection	Compliance with completing HBGM < 50% and/or No tests performed for 5 consecutive days.	None	E
C4	Medication code broken			
C4.1	Medication code broken without just cause	Medication code broken for no valid reason. Final decision at the DBL meeting (medical judgment).	PPS	E
D	Concomitant medication			
D2	Prohibited medication use			
D2.1	Rescue medication taken without just cause	Use of rescue medication (as defined in Section 4.2.1 in CTP) with FPG prior to rescue therapy ≤240 mg/dL for Visit 3 to Visit 4 or ≤200 mg/dL for Visit 5 to Visit 98 and/or Review of eCRF for use of rescue medication without 6 week dose adjustment period (i.e. prior to Visit 4).	PPS	E
D2.2	Antidiabetic drug taken that is not a protocol defined rescue medication and criterion to administer rescue medication not fulfilled	Antidiabetic drug other than protocol defined rescue medication taken and criterion for rescue therapy as in D2.1 not fulfilled.	PPS	E

* IPVs will be checked programmatically, including double programming checks for inclusion/exclusion criteria, where possible. IPVs where inclusion/exclusion criteria possibly need to be confirmed manually with respect to time A3.1, A3.4, A3.5, A4.1, A4.4, A4.5, A5.1, A5.3 and D2.3. For A1.2 dose changes may need to be checked manually. IPVs which can only be identified manually are A4.2, A4.3, A4.7, A4.8 and C3.2.

[figure not shown]
+ IPV-type: 'E' refers to efficacy IPV, 'S' refers to safety IPV and 'R' refers to general (regulatory) IPV.

